7.2. Laboratory data

Laboratory data will be evaluated to determine the incidence of abnormalities that emerge during the study. Changes in laboratory evaluations will be presented relative to baseline, which is defined as the closet visit prior to the subject start of randomized treatment. Baseline value is defined as data collected which are prior to and/or on the date of the first dose, usually also the same day as the Day 1 visit. If there is more than one value on or before Day 1, then the last non-missing value prior to (including on) the date of first randomized dose will be used as the baseline value.

Shift analyses

Each hematology, blood chemistry, coagulation parameter will be flagged as "low" or "high" relative to the parameter's normal range or as "unknown" if no results is available. All visits with available results, including unscheduled visits, will be included in shift analysis.

For each urinalysis laboratory parameter, the number and percentage of participants experiencing post-dosing shifts to abnormal will be summarized.

Each hematology and chemistry value will be flagged as "low", "normal", or "high" relative to the normal ranges of the laboratory that performed the assay, or as "unknown" if no result is available. Each urinalysis value will be flagged as "positive", "negative", or "unknown" if no value is available.

Shift from baseline to high/low status for hematology and chemistry parameters and shifts from baseline to high/positive for urinalysis will be presented. In each summary, the denominator for

the percentage is the number of patients at risk for the shift. The number at risk for a shift to low is the number of subjects whose baseline value was not low and who had at least one post-baseline value. The number at risk for a shift to high is the number of subjects whose baseline value was not high and who had at least one post-baseline value. Subjects will be counted only once for each parameter and each type of shift regardless of how many post-dosing assessments had that type of shift. A shift to high includes normal to high, low to high, and unknown to high; a shift to low includes normal to low, high to low, and unknown to low. A shift to positive includes 'negative' to 'positive' and 'unknown' to 'positive'.

Summary of change from baseline and other analyses

In addition to the shift analysis, descriptive statistics (N, mean, SD, median, 1st and 3rd quartiles, and minimum and maximum values) for observed laboratory values, change from baseline and percentage change from baseline in laboratory values of hematology, blood chemistry, and coagulation will be summarized by treatment group and visit. Hematology box and whisker plots will be presented. Only scheduled visits will be included in these summaries.

A listing of abnormal values will also be presented.

7.3. Vital signs

Summary statistical for actual values and change from baseline will be presented for each visit and vital sign parameters (temperature, pulse rate, respiratory rate, systolic and diastolic blood pressure). Weight will be summarized along with vital signs. For triplicate blood pressure measurements, the average of the 2nd and 3rd readings will be used for summarization. If fewer than three measurements are taken, the average of all blood pressure measurements will be used for any particular timepoint.

The incidence of potential clinically significant post baseline abnormalities will be summarized per the criteria below:

Table 5: Vital signs

Temperature	<36°C
	>38°C
Pulse	>100 beats per minute (bpm)
	<60 bpm
Systolic Blood	<90 mmHg
Pressure	>140 mmHg
	>160 mmHg
Diastolic Blood Pressure	<50 mmHg
	>90 mmHg
	>100 mmHg
Weight	7% or more increase from baseline
	7% or more decrease from baseline
Respiratory Rate	<12 breaths/min
	>20 breaths/min

A listing of vital sign data will be provided.

7.4. ECG

For the ECG analysis, the baseline is the pre-dose assessment at the randomization visit. It is the last non-missing value before the first randomized dose if a single ECG was performed. If ECGs were performed in triplicate, the average will be used for the quantitative ECG parameters, while the worst status will be used for qualitative parameters.

The number and percentage of subjects with shifts from normal at baseline to abnormal in ECG results will be summarized. The worst post-baseline ECG status will be used for each patient. If there is no ECG result at baseline, the subject will be counted in the unknown category. A shift to abnormal will include a shift from "unknown" or "normal" at baseline to "abnormal" post-baseline.

[figure not shown]
The number and percentage of subjects with a QTcF increase from baseline of, > 30 to 60 msec, and > 60 msec will be summarized. In addition, the number and percentage of subjects with absolute QTcF values post-baseline of > 450 msec for males or > 460 msec for females and any post-baseline QTcF values of > 500 msec will be summarized. Subjects evaluated will be those who have a baseline assessment and at least one post-baseline QTcF assessment.

Table 6: Pre-Specified Threshold Levels for ECG Parameters

ECG Parameter	Pre-Specified Level
PR	> 200 msec
QTcF	> 450 and ≤ 480 msec
	> 480 and ≤ 500 msec
	> 500
	Change from baseline: >30 and ≤ 60 msec
	Change from baseline: > 60 msec
Heart rate	< 40 beats/min
	> 100 beats/min

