## 5.2.5. Electrocardiogram

The 12-lead ECGs will be recorded at the times indicated in Table 4.

The ECGs will be recorded after the subject has been in the supine position for at least 5 minutes. Subjects will be instructed to remain completely stationary (no talking, laughing, deep breathing, or sleeping) during the rest period.

Triplicate ECGs, approximately 1 minute apart, for the QT/QTc using Fridericia's correction formula review will be obtained at the required nominal time points.

Baseline for clinical assessments will be those measurements obtained prior to study drug administration on Day 1. Another ECG will be performed approximately 1-hour postdose on Day 1.

Each ECG will be printed and evaluated by an appropriately qualified Investigator at the study site (the "local reader"). The local reader will sign and date each ECG and provide a global interpretation using the following categories or equivalent:

- Normal ECG
- Abnormal ECG Not clinically significant (NCS)
- Abnormal ECG CS
- Unable to evaluate

The local reader evaluations of the triplicate ECGs will be entered into the electronic source documents or eCRFs. If the global interpretation is Abnormal (NCS or CS), the local reader will provide further information (eg, sinus bradycardia, arrhythmia). Only overall diagnosis CS Abnormal ECG findings will be reported as AE.

All original ECG tracings will be retained as source documentation in the subject's records at the study site.

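### The ECG shift table in SAP 7.4 uses a single abnormal class, so worsening from a not clinically significant to a clinically significant abnormality is not counted in that table

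*SAP*

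**What the plan says.** **Protocol 5.2.5 (Electrocardiogram).** The local reader gives each tracing one of four interpretations: normal, abnormal NCS, abnormal CS, or unable to evaluate. The NCS/CS distinction is recorded, and it triggers more detail: "If the global interpretation is Abnormal (NCS or CS), the local reader will provide further information". ECGs are taken in sets of three: "Triplicate ECGs, approximately 1 minute apart". The readings are entered in the electronic source documents or eCRF.

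**SAP 7.4 (ECG).** The interpretation is summarized by one shift count: "The number and percentage of subjects with shifts from normal at baseline to abnormal in ECG results will be summarized". The count is defined by "A shift to abnormal will include a shift from 'unknown' or 'normal' at baseline to 'abnormal' post-baseline". Two rules set the status of each subject. With triplicates, the average is used for quantitative parameters, "while the worst status will be used for qualitative parameters"; this rule stands in the baseline paragraph. After baseline, "The worst post-baseline ECG status will be used for each patient". A subject with no baseline ECG result is classed as unknown. No denominator is stated for the shift percentage, and the SAP does not say where an unable-to-evaluate reading belongs.

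**Elsewhere.** SAP 7.4 also tabulates thresholds for QTcF (absolute and change), PR and heart rate. Protocol 5.2.5 sends CS abnormal ECGs to adverse event reporting. SAP 7.1 counts as treatment-emergent any event that was present before the first randomized dose and then worsened.

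**The concern.** Change from baseline in ECGs is part of the primary safety endpoint (Protocol 2.2.1.2). Sites are asked to judge whether an abnormality is clinically significant, yet the only by-arm summary of their judgement in the visible text has no place for that grade. This has two consequences. A subject who already has an NCS abnormality cannot be counted as worsening, however serious the later reading. Among subjects who can be counted, an incidental NCS reading and a CS finding each add one to the same total. A difference between arms in worsening to CS could be diluted or missed in this table.

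**Working it through.** **1. Grades against the shift rule.** The documents state no ECG figure to reproduce, so the first check is logical. That NCS and CS both fall in the SAP's abnormal class is inferred from its three-way wording (normal, unknown, abnormal); the SAP does not spell out the mapping.

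| Baseline | Worst post-baseline | Counted as a shift in SAP 7.4? |
|---|---|---|
| Normal or unknown | NCS | Yes |
| Normal or unknown | CS | Yes, not distinguished from NCS |
| NCS | CS | No |
| CS | CS | No |

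The third row is the gap. It exists for any NCS baseline, whether from one tracing or three. Worst-of-three only enlarges the group that cannot shift.

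**2. Number of tracings.** Post-baseline ECGs are taken 1 hour after the Day 1 dose and at Weeks 1, 12 and 16 (Protocol Table 4; SAP 3.1.3). That is 4 time points × 3 = 12 tracings, against 3 at baseline.

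**3. How many subjects NCS readings alone could move.** The documents give no rate, so let p be an assumed chance of an NCS reading, with 64 subjects per arm (SAP 2.4).

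- Tracings independent: labelled abnormal at baseline = 64 × [1 − (1−p)³]; NCS-only shifts = 64 × (1−p)³ × [1 − (1−p)¹²].
- Identical within a triplicate, independent between time points: 64 × p, and 64 × (1−p) × [1 − (1−p)⁴].
- Fully persistent: 64 × p, and 0 shifts.

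| p | Independent: abnormal at baseline / shifts | Identical within triplicate | Persistent |
|---|---|---|---|
| 5% | 9.1 / 25.2 | 3.2 / 11.3 | 3.2 / 0 |
| 10% | 17.3 / 33.5 | 6.4 / 19.8 | 6.4 / 0 |
| 20% | 31.2 / 30.5 | 12.8 / 30.2 | 12.8 / 0 |
| 30% | 42.0 / 21.6 | 19.2 / 34.0 | 19.2 / 0 |

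NCS-only shifts run from 0 to about 34 of 64, depending on assumptions the documents cannot settle.

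**4. What the table could show of a CS difference.** Assume a share a with persistent NCS, a sporadic NCS chance s per tracing (independent), and CS emerging in 2% on placebo and 10% on drug, unrelated to baseline status.

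- True difference in moves to CS: 64 × (0.10 − 0.02) = 5.1 (1.3 against 6.4).
- Difference in the SAP table: 64 × (1−a) × (1−s)³ × (1−s)¹² × 0.08.
- a = 40%, s = 0: 64 × 0.6 × 0.08 = 3.1.
- a = 40%, s = 5%: normal at baseline 0.6 × 0.95³ = 51%, or 32.9 of 64. Shifts are 32.9 × (1 − 0.95¹² × 0.98) = 15.5 on placebo and 32.9 × (1 − 0.95¹² × 0.90) = 16.9 on drug, a difference of 1.4.
- a = 30%, s = 2%: 64 × 0.7 × 0.98¹⁵ × 0.08 = 2.6. a = 50%, s = 10%: 64 × 0.5 × 0.90¹⁵ × 0.08 = 0.5.

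**5. Share due to worst-of-three.** At a = 40%, s = 5%, a single baseline tracing would leave 0.6 × 0.95 = 57% normal, or 36.5 of 64, against 32.9. The rule accounts for about 4 subjects per arm.

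**The case against.** The strongest reply is that a worsening ECG is not lost. CS findings must be reported as adverse events, SAP 7.1 treats worsened pre-existing events as treatment-emergent, and these are tabulated by arm by system organ class, preferred term and maximum severity. Measured intervals have their own thresholds, with triplicates averaged and no NCS/CS merging. Protocol 8.4.8 asks only for changes from baseline to be summarized, and no safety testing is planned. All of this stands. A reader might infer from SAP 7.4 that NCS-to-CS worsening is never counted anywhere; the documents do not support that.

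The adverse event route is still not a substitute for the count. Protocol 6.3.1 says accompanying ECG findings are not recorded as additional events, and 6.3.2 says that only the overall diagnosis is reported where there is one. CS readings are therefore spread over diagnoses, and interval thresholds do not carry the reader's overall interpretation.

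A reader might also infer that NCS readings will swamp CS findings. That needs rates the documents do not give. It also depends on how alike tracings 1 minute apart are: under full persistence there are no NCS-only shifts at all. The most that can be said is that they may obscure CS shifts.

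Finally, a figure is missing from the text of SAP 7.4 just after the shift definition, and nothing absent for that reason is held against the plan.

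**Conclusion.** The gap is real and follows from the wording, given the inference that NCS and CS both map to abnormal. The table cannot show NCS-to-CS worsening and cannot separate new CS from new NCS. No planned output visible in the documents gives a by-arm count of ECG interpretation worsening to CS. A missing denominator and an unmapped unable-to-evaluate category add to this; by contrast, SAP 7.2 defines an at-risk denominator for laboratory shifts, and SAP 7.4 defines an evaluable set for QTcF.

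The size is illustrative only. Under the assumed rates in the working, the table shows a difference of about 0.5 to 3 subjects against a true 5 per 64; all of those rates, including the drug effect, are assumptions. Worst-of-three is a secondary contributor. This is a worthwhile improvement to a descriptive safety table. It does not affect efficacy inference, and it does not mean that CS events go unreported.

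**What to change.** In SAP 7.4, replace the shift count with a cross-tabulation for each arm: baseline category (normal, abnormal NCS, abnormal CS, unknown or unable to evaluate) by worst post-baseline category. Show new or worsened CS on its own row. Its denominator should be subjects who are not CS at baseline and have at least one post-baseline ECG. State that unable-to-evaluate readings are grouped with unknown.

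Apply the same triplicate rule at baseline and at each post-baseline time point. Do not use a 2-of-3 majority at baseline alone. With a = 40% and s = 5%, the majority rule would leave 64 × 0.6 × (0.95³ + 3 × 0.05 × 0.95²) = 38.1 subjects normal at baseline instead of 32.9. Set against a worst-of-12 status (chance 1 − 0.95¹² = 0.46), purely sporadic shifts would then rise from about 15 to 17.5 per arm. A majority is also undefined when the three readings all differ.

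The cost is one table shell and one derivation from categories already collected. The downside is a slightly larger descriptive table.

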7.5. Physical examination

Abnormal findings which are noted after subjects received study treatment and are deemed by the investigator as clinically significant will be reported as AEs and included in AE analyses.

9. Changes from Protocol-Specified Analyses

The protocol definition of the intent-to-treat analysis set is all randomized subjects, however, for the definition in this SAP, ITT analysis set is defined as all randomized subjects who receive at least 1 dose of randomized study drug.

10. References

901-C-2102 Protocol V4.0 final 09May2024

901-C-2102 Protocol V3.0 08Feb2023

11. Appendices

Product: RTA 901 (BIIB143)

Study: 901-C-2102

Statistical Analysis Plan

Version: 1.0

Product: RTA 901 (BIIB143) **Study:** 901-C-2102

Statistical Analysis Plan Version: 1.0 **Product:** RTA 901 (BIIB143) **Study:** 901-C-2102

Statistical Analysis Plan Version: 1.0

